By definition, vestibulodynia, a manifestation of Genito-pelvic Pain/Penetration Disorder, a Female Sexual Disorder must be of significant to severe pain that causes a woman distress with a duration of at least 3 months. The Numerical Rating Scale, pain scale, establishes that they meet the criteria of significant to severe pain to be included in the study. The Vulvovaginal Symptoms Questionnaire characterizes qualities of the pain. The Sexual Distress Scale-Revised demonstrates whether that the pain is significant enough to cause a women distress.

The Female Sexual Function Index corroborates the existence of the pain and its effect on a woman's sexual function in 6 areas: sexual interest, sexual arousal, lubrication, orgasm, satisfaction, and pain. These questionnaires are standard of care. None of these questionnaires are experimental.

No costs will be incurred by the subjects. The Sponsor is funding the costs of the procedures.

Background:

There is no known effective treatment for secondary provoked vestibulodynia and therefore a review of the literature is relevant only to illustrate what has not been effective in alleviating this common human malady. The National Vulvodynia Society and its website contains extensive documentation of the condition and accompanying literature relevant to the epidemiology, characterization and ineffective or marginally effective treatments.

3. OBJECTIVES:

The main objective in this study is to demonstrate whether topical 10% sinecatechins ointment is significantly more efficacious than placebo in alleviating or curing significant to severe vulvar pain due to secondary provoked vestibulodynia, as the most bothersome symptom, in post-menopausal women with evidence of estrogen deficiency (vulvovaginal atrophy) without estrogenic effects on their vaginal epithelium.

4. SUBJECT SELECTION:

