13. At this visit, the study coordinator or other designated study personnel should read the SAL instructions to the patient and ask her if she has any questions. At the end of the initial visit, each patient will be given instructions that they will receive an email in order to fill out questionnaires online at the end of week 1 (one) , and week 3 (three) to be completed at home, at the end of Day 7 of those weeks, during the treatment period. They will receive a final email at the end of week 6 with instructions to fill out questionnaires anonymously online.

14. All questionnaires, both in clinic and at home, should be completed by each patient, on her own, in a private place. The patient will turn in the completed questionnaires over to the Investigator, with the option of inserting the questionnaire into an envelope which will be labeled with the patient number, name of the questionnaire and visit number. This will be done to enhance the confidentiality of questionnaires for the patient. The Investigator will fax the documents to the Sponsor via the IRIS Imaging System. Originals will be retained at the site. Alternatively, the subject may fill out the questionnaires on the secure, HIPAA compliant, website.
15. The vaginal pH, pH should indicate non-estrogenized vaginal epithelium according to the state criteria. bacterial screen results must be reviewed, signed, and dated by the Investigator prior to dispensing the study medication.

Patients will be enrolled in the study and randomized to treatment only after all the inclusion and exclusion criteria have been satisfied.

At the end of Visit 1, Week 0, site personnel will obtain investigational medication from IVRS and patients will receive a 2-week, 15 gram, supply of the investigational drug or the placebo (“the ointment”). They will be instructed on how to apply “the ointment”. They will be given written instructions on how to apply the ointment.

Instruction Sheet for Use of “The Ointment”:

- Use “the ointment” only on the area affected exactly as indicated by your clinical trial gynecologist.
- Wash your hands before and after application of the ointment. A small amount ½ inch of the ointment should be applied to the affected area using your finger(s), dabbing it on to ensure complete coverage and leaving a thin layer of the ointment as directed by your clinical trial gynecologist.

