- Apply the ointment once a day; if any irritation occurs stop using the ointment and notify your clinical trial gynecologist Do not restart to use the ointment until your irritation completely resolves. You will then be instructed to reduce the frequency of application to twice per week or less depending on your discussion with and instructions from your clinical trial gynecologist .
- Do not wash off the ointment from the treated area before the next application. When you wash the treatment area or bathe, apply the ointment afterwards, not before.
- Treatment with the ointment should be continued for a total of 4 weeks as instructed by your clinical trial gynecologist.. You will be seen at regular intervals during this time period by your clinical trial gynecologist.

•The ointment is not a cure for any condition and your condition may reoccur during or after treatment and may need further treatment.

What should I avoid while using catechins ointment?

- Do not apply the ointment on open wounds.
- While being treated with the ointment, and you do choose to have sexual contact, (genital, anal or oral) note that the ointment may weaken condoms and vaginal diaphragms therefore you must wash off the ointment carefully before having protected sexual contact. Talk to your doctor about safe sex practices.
- Avoid contact with your eyes, nostrils and mouth while ointment is on your finger(s).
- Do not expose the genital area treated with the ointment to sunlight, sunlamps or tanning beds.
- Do not cover the treated area. Loose-fitting undergarments can be worn after the ointment

PLEASE NOTE• The ointment is naturally a light reddish-tan color and therefore may stain your light-colored clothes and bedding. It is recommended to wear darker colored undergarments or an unscented disposable cotton panty liner while using the ointment.

How should I store catechins ointment?

- Store the ointment refrigerated or up to 77°F (25°C). • Do not freeze the ointment.
- Make sure the cap on the tube is tightly closed.
- Bring the tube of the ointment when you come to your scheduled clinic study visits.

Keep all medicines out of the reach of children. Do not give the ointment to other people, even if they have the same symptoms.

All subsequent visit dates for the treatment period will be calculated from Week 0 (Visit 1) date.

Week 2 (Visit 2)

The following procedures will be performed at the study clinic at the end of Week 2:

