Distribution of new copies of the SAL, FSFI, NRS, VVSQ, FSDQ-R, a question about any change in medications, along with self-addressed envelopes which will be labeled with the patient number for their return to the Investigator. Instructions will be given to complete the questionnaires at the conclusion of week 6 .

Alternatively, subject will be filling out questionnaires on secure, HIPAA compliant, website.

Consent Protocol:

Subjects will be given a written description of the study and possible untoward effects of the protocol. They will sign the IRB-approved informed consent.

Accepted subjects will be randomized and only a non-participant in the clinical trial will hold the code. Except for subjects who are excused from the trial prior to its completion because of any adverse reaction (i.e. irritation) the code will not be broken prior to the completion of the last subject's protocol.

Subjects will be consented at the initial study visit by the clinical trial gynecologist.. The clinical trial gynecologist will be available for consent discussion.

The Study Treatment: Drugs – The 10% GTO (10% 7.5% sinecatechins ointment, diluted Veregen ®) in petrolatum ointment will be furnished by Town Total Compounding Center Pharmacy ([name]), at week 0, in numbered, but otherwise unmarked compressible opaque, 15 gram tubes that will be examined at each visit. The placebo will be petrolatum ointment with an inert vegetable dye to visually appear the same as the drug. Subjects will be instructed to bring in their tubes at their 2 and 4 -week visits. The subjects will be instructed in the application of one ½ inch strand of either the study drug: 10% (diluted Veregen) or placebo once daily to the vulvar vestibule. Application – Subjects will be instructed to apply a ½ inch strand, lightly to painful or reddened areas of the vulvar vestibule. This is done daily for four weeks. Subjects will apply with a fingertip, taking care to avoid placing it into the vagina. (detailed instructions provided in this document) .

Compliance: At each visit the tubes will be weighed.

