The power analyses were based on previous research data on the effectiveness of the off label use of dilute Veregen (5% sinecatechins ointment) green tea extract (GTE) for the treatment of significant to severe vulvar pain (Patent US 2016/0271102 A1).

Statistical Analyses

Participants randomized to the dilute Veregen (10% sinecatechins ointment) green tea extract (GTE) arm will be compared to those randomized to placebo arm on demographic, descriptive and clinical variables at baseline using chi-square analysis for categorical variables, Student t test and ANOVA test for parametric data and Mann-Whitney U test for nonparametric data.

The ordinal variables (scores from the FSFI, Sexual Distress Scale revised, and the Sexual Activity Log questionnaires) will be analyzed using ANOVA test.

The nominal variables (binary categories from the Vulvovaginal Symptom Questionnaire, Erythema presence/absence and the Sexual Activities Log) will be analyzed using chi-square test. The p-values of less than 0.05 will be considered as statistically significant. These measures will be analyzed at the following assessment points (baseline, 2-week visit, 4-week visit, and 6-week follow-up).

10. IRB Review/Ethics/Informed Consent: Please see attached Informed Consent Document submitted.

IRB Review/Ethics/Informed Consent

This study will be conducted in accordance with the ethical principles that have their origin in the Declaration of Helsinki and that are consistent with Good Clinical Practice and applicable regulatory requirements. The study will be conducted in accordance with the regulations of the United States Food and Drug Administration (FDA) as described in 21 CFR 50 and 56 [add 312 for IND studies or 812 for device studies], applicable laws and the IRB requirements.

The Sponsor will submit any change to the protocol to the IRB for review and approval before implementation. A protocol change intended to eliminate an apparent immediate hazard to subjects will be implemented immediately provided the FDA and the reviewing IRB are notified within 10 working days.

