12. Intended Use of the Data: Should the study confirm the efficacy of 10% sinocatechins ointment (diluted Veregen®) in relieving or curing secondary provoked vestibulodynia in post-menopausal women without any significant effect on the maturation of the vaginal epithelium an excellent option will be available for women who suffer with this life altering condition. It would be a therapeutic option for postmenopausal women especially who because of a past history of gynecologic malignancy would be unwilling or unable to use estrogens A paper may be formulated and presented for publication in the medical literature.

The data is intended to test and therefore confirm the efficacy of local 10% sinocatechins ointment (Green Tea ointment) in the reduction or elimination of secondary provoked vestibulodynia with the added benefits of increasing lubrication and improving sexual function without demonstrable effects on the vaginal epithelium.

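### The objective and intended use include 'curing', but the design can support only alleviation and an early self-reported look after treatment; separately, the week-6 web form is called anonymous although its data must be linked

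*Combined protocol and SAP*

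**What the plan says.** **The claim.** The main objective (section 3) is to show whether the ointment is better than placebo in "alleviating or curing significant to severe vulvar pain due to secondary provoked vestibulodynia". Section 12, on intended use, looks ahead to confirmed efficacy in "relieving or curing secondary provoked vestibulodynia in post-menopausal women". The synopsis introduction and the last paragraph of section 12 also speak of eliminating the condition. The Study Design paragraph of the synopsis speaks only of alleviating pain. The instruction sheet given to subjects (section 5) says: "The ointment is not a cure for any condition and your condition may reoccur during or after treatment".

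**The measurements.** Treatment is scheduled for 4 weeks. The Q-tip test is done at screening and at weeks 0, 2 and 4 (section 5). The only later contact that the text describes is a remote set of questionnaires at week 6: SAL, FSFI, pain NRS, VVSQ, the distress scale and a question on medication changes.

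**The week-6 forms.** Section 5, Visit 1, item 13, says of the web route: "They will receive a final email at the end of week 6 with instructions to fill out questionnaires anonymously online". The Week 4 (Visit 3) text provides paper copies with "self-addressed envelopes which will be labeled with the patient number for their return to the Investigator", or completion on the secure website. Section 11(f) requires a unique numerical code on all of a subject's study records.

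**The analysis.** Section 9 gives the assessment points as "baseline, 2-week visit, 4-week visit, and 6-week follow-up".

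**The concern.** There are two separate problems.

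First, the objective contains a claim that no planned measurement can test. Cure needs a definition: how little pain, measured how, and for how long after stopping. The plan gives none. A favourable result obtained while the ointment was being applied would meet an objective whose wording includes cure, and could be reported in those terms.

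Second, week 6 is the only planned source of off-treatment data. A form that is truly anonymous cannot be matched to a randomized arm or to the woman's own baseline. If only paper returns can be linked, the analysable set depends on which route each woman used. That choice comes after randomization and could be related to how she fared. The loss could not be repaired afterwards.

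**Working it through.** **1. The plan's own figure.** Section 9 gives 28 + 28 = 56 evaluable women, 80% power, two-sided 0.05, for a 2.0-point mean difference. No SD is stated, so 56 cannot be reproduced directly. Solving for the SD that it implies:

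- Normal approximation: SD = 2.0 / [(1.960 + 0.842) × √(2/28)] = 2.67.
- Exact t test: standardized difference 0.762, so SD = 2.0 / 0.762 = 2.62.

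The sizing therefore answers a question about mean pain. Nothing in it refers to a proportion cured.

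**2. What a 2-point reduction means.** Entry requires an NRS of at least 7 on the Q-tip test (section 4). Section 9 treats a 2-point reduction as clinically important. From the entry range of 7 to 10, that gives 7 − 2 = 5 up to 10 − 2 = 8, which the plan's own bands call moderate to significant pain. The 2.0 in the power calculation is a difference between arms, so women on active treatment may fall by more than this. The target itself, however, is compatible with no woman being pain-free.

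**3. Illustration: 28 per arm on a binary cure endpoint.** The cure rates are assumed; the documents give none. Power = Φ{[|p1 − p0| − 1.960 × √(2p̄(1 − p̄)/28)] / √([p1(1 − p1) + p0(1 − p0)]/28)}.

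- 10% vs 30%: 46%
- 20% vs 50%: 66%
- 10% vs 40%: 75%
- 10% vs 50%: 93%

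Power could be low or adequate depending on the rates. The point is only that the sample size was not chosen for this endpoint.

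**4. Off-treatment window.** Week 6 − week 4 = 2 weeks after scheduled treatment ends. Q-tip tests scheduled after week 4: none. The schedule table, which is broken in the available text, also shows a column headed 12 with a mail-in entry. The text describes no week-12 contact, so I have not counted it as follow-up.

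**5. Linkage, side by side.**

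- Visit 1, item 13: week-6 web form completed anonymously. The same item describes the week-1 and week-3 web forms without that word.
- Week 4 (Visit 3): paper return carries the patient number; the secure website is the alternative, with no mention of anonymity.
- Section 11(f): code on all subject records.
- Section 9: analysis at the 6-week follow-up.

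If w is the share of week-6 responders who use the web and M the number of responders, the unlinkable records under the literal reading are w × M. With w = 0 this is none; with w = 1 it is all of M. The documents give no value for w.

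**6. What section 9 analyses at week 6.** The measures named are FSFI, the distress scale, SAL, VVSQ and erythema. The pain NRS is collected at week 6 but is not named among them. Erythema is named, although there is no examination at week 6 to record it.

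**The case against.** *Alleviation is enough to meet the objective.* The objective is worded as an either/or, it asks whether efficacy can be shown, and section 12 is conditional on success. No cure analysis is planned, and the instruction sheet may be no more than ordinary caution to subjects. This stands in part: alleviation remains testable and the trial needs no redesign. It does not justify keeping an undefined term in the objective.

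*Off-treatment pain is measured.* A reader might infer that nothing about persistence can be learned. The documents do not support that. Week 6 includes the self-reported pain NRS, and inclusion criterion 4 expects women to remain sexually active through that follow-up. With linked responses, the arms can be compared 2 weeks after scheduled treatment ends. Only longer persistence and provoked pain on Q-tip testing off treatment are out of reach.

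*The word may only mean without a name.* The invitation goes to each woman by email, and section 11(f) says that subjects are identified by code instead of by name. Read together, the intended meaning may well be coded and confidential. This stands as a plausible reading, so the defect is a contradiction to reconcile and not a demonstrated loss of data. A site or web supplier following item 13 alone could still build a form that carries no identifier.

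*No size can be put on the loss.* Correct. Any particular web share would be invented. The 3 months in the case definition is an entry duration, so the documents do not make it a yardstick for the length of follow-up.

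**Conclusion.** The point holds in a limited form. As designed, the trial can support a claim of alleviation during 4 weeks of treatment and, if week-6 responses are linked, a comparison of self-reported pain 2 weeks after scheduled treatment ends. It cannot support cure, longer persistence, or absence of Q-tip pain off treatment.

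The anonymity instruction contradicts two other provisions of the same protocol. Its effect runs from none to all of the week-6 records, depending on web use and on whether the word is applied literally.

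Neither problem touches the on-treatment pain comparison. I take that to be the powered one; section 9 does not state its time point. A reader might go further and conclude that the objective as a whole is untestable or that the week-6 data are already lost. The either/or wording and the coding rule in section 11(f) do not support either conclusion. The changes should still be made, because they decide what may be claimed and whether the only off-treatment data can be used.

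**What to change.** 1. **Sections 3 and 12:** delete the reference to curing. Align the elimination wording in the synopsis introduction and in the last paragraph of section 12, so that the claim throughout is reduction of provoked vestibular pain. If the sponsor wants to keep cure, it needs a pain threshold, a required duration and an off-treatment assessment to match, which is a larger change.
2. **Section 5, Visit 1, item 13:** replace anonymous completion with completion under the patient number on the secure website, consistent with the Week 4 (Visit 3) text and section 11(f).
3. **Section 9:** name the week-6 NRS pain comparison between arms as a secondary or descriptive analysis of early persistence, and remove erythema from the week-6 measures.

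Cost: wording changes and a coded link for the week-6 web form. No visit or procedure is added. The downsides are a narrower claim and slightly less privacy than a fully anonymous form would give.

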5. Have evidence of clinically significant organic disorder on the history and/or physical examination that would, in the opinion of the Investigator, put the patient at risk, prevent the patient from completing the study, or otherwise affect the outcome of the study.
6. Have a history of genital herpes because of the episodic nature of genital herpes and of the known possibility of occurrence of herpetic pain without visible dermatologic manifestations of herpes. Genital herpes and its accompanying genital pain may obscure the source of the genital pain experienced and confound the ability to determine the efficacy of treatment/placebo on endpoint of alleviation of pain in women with SPVD.
7. Have any infection of the genitalia
8. Have lichen sclerosis, lichen planus, contact dermatitis, psoriasis or any inflammatory condition or abrasions of the vulva
9. Have an episiotomy scar in the area where pain is perceived as it may confound the etiology of the perceived pain
10. Have diabetes.

5. STUDY PROCEDURES:

Duration of Study:

Once subjects are screened and enrolled into the study, the duration of participation in the study will be 4 weeks from the beginning of the study to the last visit. Follow up questionnaires will be filled out at 6 weeks and electronically entered or mailed in to your clinical trial gynecologist's study clinic office.

Subjects will be given a written description of the study and possible untoward effects of the protocol. They will sign the IRB-approved informed consent. The schedule and activities of visits will be given to the subject, along with instructions about notification in case of untoward events.

Accepted subjects will be randomized and only a non-participant in the clinical trial will hold the code. Except for subjects who decide to leave the trial because of any adverse reactions (i.e.. irritation), prior to its completion, the code will not be broken prior to the completion of the last subject's protocol.

Study Procedures:

Each and every procedure performed is a standard procedure. These procedures will be performed at a screening visit and each of the three subsequent study clinic visits. Initial screening; week 0, week 2; week 4 . Please note, in addition to study related procedures that a standard of care medical history, including past and current medical history, medications, allergies, height, weight and blood pressure will be taken initially and reviewed for any changes on each study clinic visit.

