6. Risks/Safety Information- The risks of full strength topical Veregen® (15% sinecatechins ointment) are well known and well documented in the accompanying package insert. Veregen® Medigene, (Green Tea ointment, (GTO), 15% sinecatechins) is a topical FDA approved drug (2006) indicated for the treatment of external genital warts, since 2006. The package insert specifies it to be applied to each and every visible wart three times a day. The safety profile for Veregen® has been well established. The application of one ½ inch strand of 10% (diluted Veregen) once daily to the vulvar vestibule does not cause the potential irritation that multiple 0.5cm strands of 15% (full strength Veregen) can cause.

The use of significantly lesser doses of the drug (one ½ inch strand), once a day vs the use of multiple 0.5cm strands three times a day and use of a lower concentration of the study drug 10% sinecatechins will significantly reduce the risk of adverse reactions to the drug as seen in the on-label use of the marketed drug Veregen® 15% sinecatechins. In fact, the use of 10% sinecatechins, ½ inch strand, topically applied, once daily to the vulvar vestibule was found to be soothing, and reduced or eliminated vulvar pain in post-menopausal women with secondary provoked vestibulodynia (SPVD).

In Phase 3 clinical trials, a total of 397 subjects received Veregen® (15% sinecatechins) three times per day topical application for the treatment of external genital and perianal warts for up to 16 weeks.

Local irritation is the main potential side effect and in fact the goal of treatment of external genital warts with full strength Veregen (15% sinecatechins ointment) by simultaneously applying a 0.5cm strand to each and every one of multiple visible genital warts three times daily for up to 16 weeks. The mechanism of action of Veregen in clearing genital warts is unknown. (see package insert for Veregen). It was discovered that the off-labeled use of diluted Veregen (10% sinecatechins ointment) applied as a single ½ inch strand once daily was safe and effective in alleviating the pain from SPVD, as demonstrated in the off-labeled use of Veregen with patients in private practice as also seen with 5% sinecatechins ointment (see US Patent 9750716). The mechanism of action of Veregen for treating secondary provoked vestibulodynia (SPVD) is unknown but may be due to Veregen's (sinecatechins, green tea extract) known action as an antioxidant/anti-inflammatory.

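### The code-break exception for adverse-reaction leavers has no need condition and no limit on who is told, so it could reveal the arm of women with irritation who stay in the trial

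*Combined protocol and SAP*

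**What the plan says.** Section 1 (Study Design) describes the trial as double blinded. Section 5, under Duration of Study, says that "only a non-participant in the clinical trial will hold the code". It then keeps the code closed until the final woman has finished, apart from one group: "Except for subjects who decide to leave the trial because of any adverse reactions". The only reaction named there is irritation. The Consent Protocol in the same section repeats the rule with a different trigger, and its exception opens: "Except for subjects who are excused from the trial prior to its completion because of any adverse reaction". One wording covers women who choose to go; the other covers women whom someone releases.

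Three other places bear on this:

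- **Section 6 (Risks/Safety Information).** "Local irritation is the main potential side effect" of the 15% product as used on genital warts. The same section states that the once-daily 10% regimen does not cause that irritation.
- **Section 5 (Instruction Sheet).** A woman with irritation is to stop, notify her trial gynecologist and wait until it resolves. After that, "You will then be instructed to reduce the frequency of application to twice per week or less". She therefore stays in the trial.
- **Section 1 (Study Related Procedures) and section 5 (Study Procedures).** The trial gynecologist and assistants perform the Q-tip test, record the pain intensity and note erythema at each clinic visit. No independent assessor is named.

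**The concern.** The exception is tied to the event most likely to distinguish the arms. The placebo is dyed petrolatum matched on appearance, so irritation is a natural clue to active ointment. Opening the code for women who leave with irritation could confirm that clue. The women who leave are not the main problem. Others with irritation remain on a reduced schedule and are still examined by staff at the same site. Staff who have learned that irritation leavers were on active ointment can apply that knowledge to the women who stay.

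At stake are the site-elicited outcomes. The woman gives the Q-tip number, but staff provoke the pain, ask for the rating and write it down. Erythema is judged by staff outright. Both are open to expectation, and the exception gives the comparison nothing in return.

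**Working it through.** The plan states no figure for this point, so the main check is a reading of the text.

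**Step 1: what the rule requires.** Both statements are exceptions to a no-break rule. They lift the ban for adverse-reaction leavers without commanding a break. They give no criterion for choosing among such women.

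**Step 2: who learns the result.** The holder is a non-participant. Nothing says whether the woman, the gynecologist or the sponsor is told after a break, and nothing keeps the result from the Q-tip examiner.

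**Step 3: who could be affected.** The Instruction Sheet creates a group with irritation that remains under assessment. Leakage to that group needs three things: some leavers' codes are opened, site staff hear the result, and irritation is more common on active ointment. The documents neither establish nor rule out any of the three.

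**Step 4: which outcome is exposed.** Section 9 names the primary outcome only as a pain score. If it is the Q-tip rating, the route reaches it directly. If it is the diary or questionnaire NRS, which the woman completes alone, the route through the examiner largely misses it. It would then reach mainly the Q-tip and erythema records.

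**Step 5: illustration of size.**

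- Inputs from section 9: difference 2.0 points, 28 per arm, two-sided 0.05, 80% power, two-sample t test, 15% withdrawal, 64 randomised.
- SD: not stated. Solving the non-central t for 80% power gives a standardised difference of 0.762, so SD = 2.0 / 0.762 = 2.62.
- Assumed, not in the documents: sites identify 10% to 30% of the remaining active women, and scores of identified women shift by 0.5 to 1.5 points.
- Bias = fraction identified × shift. Low: 0.10 × 0.5 = 0.05. High: 0.30 × 1.5 = 0.45, or 0.45 / 2.0 = 22.5% of the target difference.
- Rejection rate with no true effect: non-central t, df = 28 + 28 − 2 = 54, non-centrality = (bias / 2.62) × √(28/2).

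| Assumed bias (points) | Non-centrality | Type I error |
|---|---|---|
| 0 | 0 | 5.0% |
| 0.05 | 0.07 | 5.1% |
| 0.30 | 0.43 | 7.1% |
| 0.45 | 0.64 | 9.7% |

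The result also depends on the SD. At an assumed bias of 0.5 points the rate is 10.8% with SD 2.62, 15.1% with SD 2.0 and 9.4% with SD 3.0.

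**Step 6: number of possible breaks.** The withdrawal allowance is 0.15 × 64 = 9.6 women for all causes. The share leaving because of irritation is not given, so 9.6 is not an estimate of code-breaks.

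**The case against.** The strongest reply is that the text says less than a reader might infer from it. Four inferences are tempting:

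- **That the code is opened for every woman who leaves with irritation.** The documents give an exception, not an instruction.
- **That sites are told the result.** They do not say so, and the code sits with someone outside the trial.
- **That the study ointment is known to irritate.** Section 6 ties irritation to the 15% product applied three times a day and denies it for the 10% regimen.
- **That site staff rate the primary endpoint.** Section 9 does not say which pain score is primary, and the woman supplies the number in either case.

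All four corrections stand, and they limit the claim to a risk. They do not remove it. A permission without criteria or disclosure limits still leaves the blind to local habit. The assurance about the 10% regimen also sits beside an Instruction Sheet that plans for irritation and a code-break rule that names it.

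Two further replies stand in part. Staff are notified of irritation and could guess the arm with no code opened, so tightening the rule removes only part of the exposure. Opened codes would also include any placebo leavers, which would weaken the inference; the illustration does not model this.

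**Conclusion.** The point holds as a weakness in the blinding rule. Sections on Duration of Study and Consent Protocol exempt adverse-reaction leavers from the closed code without a need condition or a limit on disclosure, while other women with irritation remain under assessment by site staff. It would be going too far to say that the blind will be lost or that the primary analysis is biased. That would require disclosure to sites, a difference in irritation between arms and a site-elicited primary score, none of which the documents establish.

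The size of any bias is unknown. The range of 5.1% to 9.7% rests wholly on assumed identification rates and score shifts and on a back-solved SD. Its low end is negligible, and it should not be read as the effect of code-breaks alone. Severity is minor; the case for acting is that the change is cheap.

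**What to change.** In section 5, under both Duration of Study and Consent Protocol, replace the blanket exception with one identical rule:

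- An individual code is opened only when the allocation must be known for that woman's care.
- Each break is logged with date, reason and who was told.
- The result is withheld from Q-tip and erythema assessors and from continuing participants.
- The woman is analysed in her randomised arm.

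Using the same text in both places also settles whether the rule concerns women who choose to leave or women who are excused.

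The cost is two edited sentences and a log, with no added patients or visits. The small downside is that the allocation of other adverse-reaction leavers stays closed until the last subject completes. The change does not stop staff guessing the arm from irritation itself.
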